from this study is impractical and would delay and jeopardize completion of study enrollment. Multiple steps have been included in the trial design to account for the potential impact of pain from fibromyalgia on study results. To ensure that a significant component of the subjects daily pain NRS score is from inflammatory pain from joint/tendon involvements, subjects will be required to have arthritis and/or tendonitis on SELENA SLEDAI assessment or B score in the musculoskeletal domain of the BILAG 2004 assessment. The presence or absence of fibromyalgia and its severity will be assessed using the Fibromyalgia Symptom Score [107]. The absence versus presence of fibromyalgia (Fibromyalgia Symptom Score < 13 versus \geq 13 at Screening) will be used as a stratification variable at randomization and in subset analyses of the efficacy outcomes.

1.6.2 **Rationale for the Treatment Arm**

The JBT-101 doses selected for this study are within the range of doses that were well tolerated in previous Phase 1 and 2 studies and in a recently completed clinical trial in SSc, all sponsored by Corbus Pharmaceuticals Holdings, Inc. The JBT-101 oral doses selected for this study are 5 mg b.i.d., 20 mg q.d., and 20 mg b.i.d. Parallel dose assignment to JBT-101 in doses up to 20 mg b.i.d. is supported by a previous multiple ascending dose study and a Phase 2 study in humans in which JBT-101 doses up to 40 mg b.i.d. showed acceptable safety profiles and were well-tolerated. In a recently completed study of JBT-101 in systemic sclerosis and ongoing studies in dermatomyositis and cystic fibrosis (sponsored by Corbus) using similar doses to those proposed in this clinical trial (5 mg-40 mg daily), JBT-101 has been well tolerated with no severe AEs attributable to JBT-101. Each dose is expected have an acceptable safety profile, be well-tolerated, and provide clinical benefit, based on previous animal or human testing and the nature of the inflammatory components of SLE. Based on preclinical data and early higher dose clinical data, it is expected that any safety risk and clinical efficacy of JBT-101 in humans will be related to exposure. Based on extrapolation from animal models of inflammation, 5 mg q.d. was estimated to be about the median dose required for efficacy in humans. However, information from the cystic fibrosis study and from a cutaneous model of E. coli- induced inflammation [101] suggests that 5 mg b.i.d. may be more effective than the 5 mg q.d. dose:

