3.1.1 Stratification, Randomization, and Blinding

Eligible subjects will be randomized in a 1:1:1:1 ratio to one of four cohorts: 5 mg JBT-101 b.i.d., 20 mg JBT-101 q.d., 20 mg JBT-101 b.i.d., or placebo (see Section 3.1, *Description of Study Design*, Table 1). Subjects will be stratified by 7-day average of maximum daily pain NRS score ≤ 6 versus > 6 and Fibromyalgia Symptom Scale Score < 13 versus ≥ 13 at Screening.

To maintain the study blind, JBT-101 and placebo capsules and their packaging will be identical. All subjects will receive b.i.d dosing to maintain blinding to treatment assignment. In general, clinical staff, including the investigators, will be blinded to the treatment assignments until completion of the study. In addition, they will not have access to any mechanistic data, and mechanistic laboratory staff will not have access to any clinical results until completion of the study. The success of blinding will be formally tested using a Treatment Satisfaction Survey that asks each study subject and corresponding site investigator to guess the study group assignment for that subject at the end of active treatment and then comparing these responses to what would be expected by chance.

Unblinding must be approved by the study Medical Monitor unless an immediate life threatening condition has developed and the Medical Monitor is not accessible. The site investigator will notify the protocol chair(s) and the DAIT- Statistical and Clinical Coordinating Center (SACCC) of the unblinding event on the next business day. The emergency unblinding will also be reported to the Data and Safety Monitoring Board (DSMB).

A full account of the event will be recorded, including the date and time of the unblinding, the reason for the decision to unblind, and the name of the individual who made the decision and the names of the Medical Monitor and others who were notified. The reasons for unblinding of a participant's treatment will be included in the final study report.

An individual's treatment assignment will be unblinded if the subject experiences a suspected adverse reaction that is serious and unexpected (see Section 7.2.1, *Adverse Event* and Section 7.2.1.1 *Suspected Adverse Reaction* and Section 7.2.2, *Unexpected Adverse Event*) or other protocol-specific event(s) determined by DAIT/NIAID to warrant unblinding.

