4.1 Inclusion Criteria

Individuals who meet ALL of the following criteria at Screening are eligible for enrollment:

- 1. Fulfill the updated ACR 1997 Revised Criteria for the Classification of Systemic Lupus Erythematosus [108]
- 2. ≥ 18 and ≤ 70 years of age at the time the Informed Consent Form is signed
- 3. At least 3 months treatment with an anti-malarial drug such as hydroxychloroquine or a history of intolerance, contraindication, or unwillingness to take an anti-malarial drug
- 4. Meets the SELENA SLEDAI definition of arthritis [109] or moderate arthritis or tendonitis that has not improved over the last month (i.e. BILAG B on the updated BILAG 2004 [110])

- 5. Seven-day average of maximum of daily pain NRS scores ≥ 4 out of 10 during screening with continued reporting of pain NRS scores on at least 67% of days between the Screening visit and randomization.
- 6. Overlap with polymyositis, systemic sclerosis, Sjögren's syndrome, or rheumatoid arthritis is allowed, if, in the site investigator's judgment, the predominant clinical features are those of SLE
- 7. Not expected by the site investigator to require a change in potential disease-modifying treatments for SLE from Screening through Visit 6 (Day 113)
- 8. Willing to not start or stop any NSAIDs or potential disease-modifying medications or supplements for SLE from Screening through Visit 6 (Day 113), unless a change is recommended by the site investigator or other treating physicians
- 9. Willing not to use any legal or illegal cannabinoids, including FDA-approved cannabinoids or cannabinoid-mimic drugs, or any illegal substance of abuse from Screening through Visit 6 (Day 113)
- 10. If a woman of child-bearing potential, willing to use one of the highly effective (failure rate < 1% per year) birth control method from Screening through Visit 6 (Day 113) or for 28 ± 3 days after the last dose of study product (See Appendix A: Reproductive Potential and Effective Methods of Contraception)
- 11. Willing to follow instructions, complete study procedures and attend study visits as required by this protocol

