6.2 Assessments of Efficacy

6.2.1 **Primary Efficacy Variable: Maximum Daily Pain NRS Score**

Efficacy will be assessed using the maximum daily pain NRS score. The pain NRS is a single-item pain numerical rating scale for pain, which is a segmented numerical version of the visual analogue scale in which the respondent selects a whole number (0-10) that best reflects the intensity of their pain. The numerical rating score is anchored by two terms describing average pain severity extremes, one of "no pain" (score of 0) and one of "worst pain imaginable" (score of 10). The subjects will be instructed to rank their worst pain in the previous day, at about the same time each evening, so the recall period is about 24 hours of the most recent entry. The subjects will record their maximum daily pain NRS score each day using an IVRS (See Section 3.1, *Description of Study Design*.).

Site personnel will receive daily notifications indicating if subjects have not completed their most recent pain scores and they will be responsible for contacting subjects to ensure pain scores are completed regularly. Sites will also receive monthly reports on overall compliance and data integrity.

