6.2.2.2 Pain Categories

Change in pain category from baseline will be determined. Categories of pain, as defined by the 7-day average of maximum daily pain NRS, are:

- No pain: 7-day average of maximum daily pain NRS ≤ 1
- Mild pain: 7-day average of maximum daily pain NRS > 1 and ≤ 3
- Moderate pain: 7-day average of maximum daily pain NRS > 3 and ≤ 7
- Severe pain: 7-day average of maximum daily pain NRS > 7

Changes in categories of pain, as defined by the 7-day average of maximum daily pain NRS are:

- Major improvement: Improvement by at least two pain categories from baseline (Visit 1 (Day 1))
- Improvement: Improvement by one pain category from baseline (Visit 1 (Day 1))
- No change: No change in pain category from baseline (Visit 1 (Day 1))
- Worsening: Worsening by at least one pain category from baseline (Visit 1 (Day 1))

6.2.2.3 66/68 Joint Count

Determining the number of swollen joints and tender joints is a key component in the clinical assessment of active musculoskeletal disease in this study. This study will assess swelling and tenderness in 66 and tenderness in 68 joints, which includes joints in the feet. The 66/68 joint count evaluates the following joints: upper—temporomandibular, sternoclavicular, acromioclavicular, shoulder, elbow, wrist, metacarpophalangeal, proximal interphalangeal and distal interphalangeal; lower—hip, knee, ankle, tarsus, metatarsophalangeal and interphalangeal.

Swelling and tenderness are measured separately. Joint swelling is soft tissue swelling that is detectable along the joint margins. When a synovial effusion is present, it invariably means the joint is swollen. Neither bony swelling nor deformity of the joints constitutes joint swelling. Fluctuation is a characteristic feature of swollen joints and it may influence the range of joint movement.

Joint tenderness is the presence of pain in a joint at rest with pressure or on movement of the joint, e.g. on movement of the hip joints. Pressure to elicit tenderness should be exerted by the examiner's thumb and index finger sufficient to cause blanching of the examiner's nail bed.

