8.3 Description of the Analyses

- All data will be provided in data listings sorted by treatment groups, subject number, and visit.
- Summary data will be presented in tabular format by treatment groups.

- Categorical data will be summarized by the number and percentage of subjects in each category.
- Continuous data will be summarized by descriptive statistics including N, mean, standard deviation, median, and range.
- All percentages will be rounded to one decimal place.
- Differences between groups will be calculated as active placebo and change from baseline (ΔNRS) will be calculated as follow-up visit – baseline.
- The baseline measure will be defined as the last non-missing measure prior to initiation of study product. It is expected that baseline values for efficacy assessments will be measured at Visit 1 (Day 1).
- P-values will be assessed at a 2-sided alpha = 0.05 level for the primary efficacy analysis.
- Secondary analyses are exploratory and intended to deepen our understanding of risks and benefits, to refine hypotheses, and to obtain information from which to design, select doses, and power future pivotal studies. P-values will be presented for secondary efficacy analyses. No adjustments for multiple comparisons are planned for secondary analyses.

8.3.1 **Subject Disposition**

The disposition of all subjects over the course of the trial will be summarized by cohort and overall. The number and percent of subjects in each analysis population (mITT, PP, safety, and PK) will be displayed. In addition, the presentation will include the number of subjects who completed the study, the number who withdrew prematurely from the study, as well as the reason for withdrawal. In addition, the number of subjects who continued treatment to Visit 5 (Day 85) and who discontinued treatment early will also be summarized along with reasons for discontinuation.

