Analyses plans for other categorical secondary endpoints (e.g. presence/absence of arthritis on the SELENA SLEDAI or BILAG scores for the musculoskeletal domain) will be analogous to those noted in the previous paragraph. Generally, mixed models will be used to evaluate disease activity or patient-reported secondary endpoints that are indices or scores assessed at Visits 1 - 5 (Days 1 - 85). Models will be used to compare trajectories and changes in the secondary endpoints over time among the individual JBT-101 groups (Cohort 1, Cohort 2, and Cohort 3) and placebo (Cohort 4). Data transformations will be considered, as appropriate. Larger models may be constructed for these comparisons with consideration of additional covariates that are found to differ between the treatment groups. Covariates may include, but are not limited to: 7-day average of the maximum daily pain NRS score at Visit 1 (Day 1), Fibromyalgia Symptom Score at Visit 1 (Day 1), gender, age, disease duration, and severity.

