8.9 Examination of Subgroups

Exploratory subgroup analyses of efficacy endpoints will be done based on subject Screening 7-day average of the maximum daily pain NRS score ≤ 6 versus ≥ 7 and Fibromyalgia Symptom Scale score < 13 and ≥ 13 at Visit 1 (Day 1).

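### Section 8.9's pain subgroups leave Screening averages between 6 and 7 unassigned, and the fibromyalgia subgroup has two different time points

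*Protocol*

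**What the plan says.** **Pain split.** Section 8.9 bases the exploratory efficacy subgroups on "Screening 7-day average of the maximum daily pain NRS score ≤ 6 versus ≥ 7". Section 3.1.1 says subjects are "stratified by 7-day average of maximum daily pain NRS score ≤ 6 versus > 6", measured at Screening. Both sections cut the same quantity.

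**Scale.** In Section 6.2.1 "the respondent selects a whole number (0-10) that best reflects the intensity of their pain". Inclusion criterion 5 in Section 4.1 requires "Seven-day average of maximum of daily pain NRS scores ≥ 4 out of 10 during screening".

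**Other cuts of 7-day averages.** Section 6.2.2.2 sorts 7-day averages of this score into four categories that meet without gaps, for example "Moderate pain: 7-day average of maximum daily pain NRS > 3 and ≤ 7", with severe pain starting immediately above 7.

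**Fibromyalgia split.** Section 8.9 divides the Fibromyalgia Symptom Scale at 13, as measured at Visit 1. Section 1.6.1 uses the same threshold at Screening and says this classification "will be used as a stratification variable at randomization and in subset analyses of the efficacy outcomes". Section 3.1.1 also stratifies on the Screening score.

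**The concern.** A split at 6 or below versus 7 or above is complete for a single whole-number score but not for an average of seven such scores. Followed literally, 8.9 omits every subject whose Screening average lies strictly between 6 and 7. The loss is one-sided, because all of those subjects were randomised in the higher-pain stratum. The higher-pain subgroup would therefore be smaller and more extreme than the stratum it appears to represent.

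The fibromyalgia subgroup has a different problem: its membership depends on which section the analyst follows. Section 1.6.1 lists the subset analysis among the steps meant to deal with fibromyalgia pain, since patients with fibromyalgia are not excluded. The definition should therefore be settled before the data are seen.

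**Working it through.** The protocol states no figure of its own here, so the check is a count, an illustration of size, and a comparison of texts.

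**1. Count of possible averages (no distributional assumption).**
- Inputs: whole-number daily scores from 0 to 10 (6.2.1); eligibility at an average of 4 or more (4.1); seven entries.
- A full 7-day average equals k/7 for a whole number k. Eligible values run from 28/7 = 4 to 70/7 = 10, which gives 70 − 28 + 1 = 43 values.
- Strictly between 6 (42/7) and 7 (49/7) lie k = 43 to 48: 6.14, 6.29, 6.43, 6.57, 6.71 and 6.86. That is 6 values.
- Above 6: k = 43 to 70, or 28 values. At 7 or above: k = 49 to 70, or 22 values.
- Gap: 6/43 = 14% of eligible values, and 6/28 = 21% of values in the upper stratum.
- With the 3.1.1 cut, all 43 values are assigned.

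These percentages count possible values, not subjects.

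**2. Would rounding rescue the rule?** The protocol states no rounding. Rounding to the nearest whole number would close the gap, but it would send 6.14, 6.29 and 6.43 to the lower subgroup although those subjects were randomised in the upper stratum. The subgroups would still not match the strata.

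**3. Illustrative share of subjects (assumed distribution).** The protocol gives an SD of 1.3 to 1.6 for daily scores (8.1) but no Screening mean or distribution. I assumed a normal distribution placed on the 1/7 grid and truncated to 4 to 10, with parent mean 5 to 7.5. The SD range was widened to 2.0.

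| Parent mean | Gap share, SD 1.3 | Gap share, SD 1.6 | Gap share, SD 2.0 |
|---|---|---|---|
| 5.0 | 17.1% | 18.4% | 18.4% |
| 5.5 | 21.9% | 20.9% | 19.4% |
| 6.0 | 25.5% | 22.5% | 19.9% |
| 6.5 | 26.6% | 22.6% | 19.6% |
| 7.0 | 24.5% | 21.3% | 18.8% |
| 7.5 | 20.0% | 18.7% | 17.4% |

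- A middle case, mean 6 and SD 1.43 (the protocol's pooled value): 48.3% at or below 6, 24.0% unassigned, 27.7% at 7 or above. The gap is 24.0/(24.0 + 27.7) = 46% of the upper stratum.
- Across the grid, the gap takes from 23% (mean 7.5, SD 2.0) to 66% (mean 5, SD 1.3) of the upper stratum.
- Per arm of 25, at mean 5 and SD 1.3: the higher-pain group falls from about 6.4 to 25 × 0.087 = 2.2 subjects.
- Per arm of 25, at mean 7.5 and SD 1.3: it falls from 25 × 0.864 = 21.6 to 25 × 0.664 = 16.6.

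**4. Fibromyalgia time point.** The Schedule of Events (Table 3) collects the scale at both Screening and Visit 1. Visit 1 falls 7 to 42 days after the start of screening, and Section 6.4.1.1 requires randomisation at least 7 days before Visit 1. The Visit 1 score therefore cannot be the stratification value, and a subject may fall on different sides of 13 on the two occasions. The document gives nothing from which to estimate how often.

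**The case against.** **The consequence is small.** Section 8.9 calls these analyses exploratory, and 8.8 treats the p-values and confidence intervals of the secondary analyses as descriptive. Section 8.3.2.2 also plans interaction terms for the Screening average in the regression model. Those use the average without a cut point, so they omit no one. This stands, and it limits the grade. It does not close the gap in 8.9.

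**The fibromyalgia point is weaker.** Section 1.6.1 is a rationale, while Section 8 is where readers are sent for planned analyses. Visit 1 fits the baseline convention in 8.3 and the candidate covariate list in 8.3.2.2, which includes "Fibromyalgia Symptom Score at Visit 1 (Day 1), gender, age, disease duration, and severity". That is fair: 8.9 is not clearly the section in error. The two texts still disagree about the same subset analysis.

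**The size rests on assumptions.** The mean range is assumed, an SD of 2.0 lies outside the protocol's range, and the protocol's SD describes daily scores and not a truncated Screening average. The 66% and the fall from 6.4 to 2.2 come from one corner of the grid. The 43-value count also needs seven entries. Section 4.1 accepts reporting on 67% of screening days, and if an average used six or five entries the counts would be 5 of 37 or 4 of 31. All of this stands, and the gap remains in every case.

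**Another cut would also work.** Below 7 versus 7 or above would also assign everyone, and 8.9 does not say that its subgroups are the strata. That is true, but only the cut above 6 agrees with 3.1.1.

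**Conclusion.** The concern holds and is minor. As written, 8.9 leaves averages strictly between 6 and 7 in neither pain subgroup and conflicts with the cut in 3.1.1. This follows from the text alone: 6 of 43 eligible full-week values, all in the higher-pain stratum. The share of subjects affected, about 17% to 27% overall and 23% to 66% of the upper stratum, depends on an assumed Screening distribution and is only illustrative.

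The fibromyalgia subgroup has two stated time points that need reconciling. Both precede dosing, so neither choice introduces treatment-related bias, and no size can be given. The primary 3-degree-of-freedom test and the sample size are unaffected.

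**What to change.** In 8.9, define the upper pain subgroup as a Screening average above 6, so that the subgroups equal the randomisation strata in 3.1.1.

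State one fibromyalgia time point in both 1.6.1 and 8.9. Use Screening if the subgroups are meant to be the randomisation strata, as 1.6.1 says. Otherwise keep Visit 1 in 8.9 and amend 1.6.1.

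The cost is one symbol in 8.9 and one wording edit in 8.9 or 1.6.1. The scale is already collected at both visits, so no data or procedures are added.

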8.10 Changes to the Statistical Analysis Plan

A detailed description of the planned analyses will be provided in a Statistical Analysis Plan that will be completed and signed off prior to database lock. Major changes from this protocol will be noted in the Statistical Analysis Plan. Changes to the Statistical Analysis Plan that are made subsequent to database lock will be documented in the clinical study report.

8.11 Missing Data

For the primary analysis, a longitudinal mixed model is planned, which will include all available data from all subjects in the mITT population regardless of completeness. Because this is a short study, data is expected to be missing at random, but any obvious contradictions to this assumption will be noted and considered. Standard procedures will be used to ensure that data are as complete and accurate as possible. Generally, missing data will not be imputed. Deviations from this approach will be specified in the Statistical Analysis Plan.

9 ACCESS TO SOURCE DATA AND DOCUMENTS

Each participating site will maintain the highest degree of confidentiality permitted for the clinical and research information obtained from subjects participating in this clinical trial. Medical and research records should be maintained at each site in the strictest confidence. However, as a part of the quality assurance and legal responsibilities of an investigation, each site must permit authorized representatives of the IND sponsor(s), the DAIT-SACCC, Corbus Pharmaceuticals Holdings, Inc., and health authorities to examine (and when required by applicable law, to copy) clinical records for the purposes of quality assurance reviews, audits, and evaluation of the study safety and progress. Unless required by the laws permitting copying of records, only the coded identity associated with documents or other subject data may be copied (obscuring any personally identifying information). Authorized representatives as noted above are bound to maintain the strict confidentiality of medical and research information that may be linked to identified individuals. Participating sites will normally be notified in advance of auditing visits.

All subject records and study documentation will be kept after the protocol is completed. This will include all documentation of AEs, records of study drug receipt and dispensation, and all IRB correspondence. All study records will be kept for at least two years after the investigation is completed.

10 DATA COLLECTION, QUALITY CONTROL AND QUALITY ASSURANCE

The investigator is required to keep accurate records to ensure the conduct of the study is fully documented. The period of record retention should be consistent with the record retention policies of the sponsoring agency or applicable regulatory agencies. However, in certain instances, documents should be retained for a longer period if required by the applicable regulatory agency or by the National Institutes of Health.

The investigator will report all major protocol deviations to DAIT and the DAIT-SACCC per the instructions in the Autoimmunity Centers of Excellence (ACE) Manual of Procedures. The DAIT-SACCC will forward reports of protocol deviations to the responsible DAIT/NIAID medical officer for review as specified in the Manual of Procedures.

The DAIT-SACCC is responsible for regular inspection of the conduct of the trial, for verifying adherence to the protocol, and for confirming the completeness, consistency, and accuracy of all documented data.

Data will be obtained from a variety of sources including, but not limited to laboratory notebooks, automated instrument output files, and clinical subject charts. Data from these source materials will be transmitted to the DAIT-SACCC via one of two mechanisms. Data collected electronically at central laboratories will be transferred electronically directly from the laboratory to the DAIT-SACCC using standard secure data transfer procedures. Data collected at the clinical sites will be transmitted to the DAIT-SACCC using an internet-based remote data entry system. Clinical site personnel use an internet browser to key data into eCRFs; each CRF page is submitted to the clinical database electronically as the page is completed. Univariate data validation tests are performed as the data are keyed. The clinical database is backed up nightly; backup tapes are saved in a secure, off-site location. At any time, authorized site personnel may log in to the remote data entry system, review and correct previously entered data, or key additional data. The data will be further validated per the study data validation plan via a series of computerized and manual edit checks, and all relevant data queries will be raised and resolved on an ongoing basis. Complete, clean data will be frozen to prevent further inadvertent modifications. All discrepancies will be reviewed and any resulting queries will be resolved with the investigators and amended in the database. All elements of data entry (i.e., time, date, verbatim text, and the person performing the data entry) will be recorded in an electronic audit trail to allow all data changes in the database to be monitored and maintained in accordance with federal regulations.

The DAIT-SACCC will periodically visit the participating clinical sites and audit the source documents in order to validate the data in the DAIT-SACCC central database. Data will be provided using the subject's screening or enrollment number, the DAIT-SACCC will not collect personally identifying information such as the subject's name or social security number. Subjects will provide demographic information such as race, ethnicity, and birth date.

Data collected by the DAIT-SACCC will be held in the strictest confidence, and are protected from access that could reveal personally identifying information about any subject in the trial.

